5. SAMPLE SIZE, RECRUITMENT, RANDOMISATION, AND BLINDING

5.1 Sample size and power

Population Evaluation

Pseudo-anonymised data from all children (<16 years) within participating practices will be used to analyse the impact of the CYPHP Evelina London model on health service use.

11 clusters in each arm, and an average of 3800 CYP per cluster, provides over 87% power to detect a reduction of 20% in the rate of non-elective admissions, assuming a coefficient of variation of 0.142, as explained below.

The number of CYP per cluster is estimated conservatively based on the 89382 CYP (age 0-15) registered in 2015 in the GP practices in the 23 randomised clusters. For each financial year 2013-14 – 2015-16, the baseline rate of non-elective admissions and the coefficient of variation was estimated using counts of non-elective admissions per cluster from financial years 2013-14 – 2015-16, and counts of CYP enrolled per cluster during 2013-2015. The coefficient of variation used in the sample size calculation was the mean of these three estimates. The rate of non-elective admissions was the total rate estimated by combining data from the three financial years.

Tracer Condition Evaluation

With 11 clusters in each study arm, the study team will need to recruit a minimum of 1006 CYP with a long-term tracer condition (asthma, constipation or eczema) per arm (total 2012). This number of participants will give the study 90% power to detect a mean minimum clinically important difference (MCID) of 4.5 points (standard deviation 16.5) in the primary child-health outcome tool (parental reported PEDSQL (Varni et al, 1999),² as used previously with children with chronic health conditions such as asthma (Varni et al, 2004).⁸ Intraclass coefficient (ICC) is assumed to be 0.02 based on study of quality of life in children and young people with a related condition, hay fever (Hammersley et al, 2010). Inter-cluster variation is assumed to be (0.03) based on the harmonic mean and variance of cluster size derived from GP registrations. This number also accounts for a 30% loss to follow up.

In total there are **23 clusters**, 12 in one arm and 11 in the other. As such the outlined sample size underestimates the total power as we have assumed 11 clusters in each arm.

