10.9 Health Service Use Analysis Methods

The population analyses will assess the effects of the CYPHP model on health service use for CYP with any (or no) health condition.

Main analysis: cRCT Intervention vs. control analysis

- Populations: See section 8
- Time period: See section 7
- Comparator: Study arm (Intervention vs Control)
- Endpoints: Rates of health service use (listed and defined in sections 9-10)
- Summary statistics: estimate of intervention effect, estimates of covariate coefficients, 95% confidence intervals, p-values

Formal analysis: Multi-level Poisson regression model

- Individual level covariates: age, sex, IMD 2015, IDACI 2015, Borough
- Cluster level covariates: IMD 2015, IDACI 2015, baseline rate of health service use endpoint, number of CYP under 16 per cluster, Rate of paediatric OP referrals 2015-16, Borough
- Data structure:
 - Individual data: Pt Identifier, Cluster, Study arm (Intervention/Control), Number of HSU events during observation period, Observation time (days), Rate of HSU events during trial, Age at baseline, Sex, IMD 2015, IDACI 2015, Borough of GP registration, Number of HSU events during baseline period, Length of baseline period (days), Baseline rate of HSU events
 - Cluster data: IMD 2015, IDACI 2015, baseline rate of health service use endpoint, number of CYP under 16 per cluster, Rate of paediatric OP referrals 2015-16, Borough

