11.9 Analysis Methods

Analysis (for 6-month and 12-month follow-up): Random-effects regression models. Covariates at individual level: participant age group, sex, IMD 2015 quintile, IDACI 2015 quintile, Borough, and the baseline questionnaire outcome score. Covariates at cluster level: mean IMD 2015, mean IDACI 2015, number of children under 16 years, rate of paediatric OP referrals 2015-16, and the mean baseline questionnaire outcome score.

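### SAP 10.9 holds each child's own baseline service use but leaves it out of the model; adding it would sharpen the equity interactions and, depending on how the cluster baseline rate is built, the tracer arm effects modestly

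*SAP*

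**What the plan says.** Section 10.9 names the model ("Formal analysis: Multi-level Poisson regression model") and two sets of covariates. At child level: "Individual level covariates: age, sex, IMD 2015, IDACI 2015, Borough". At cluster level the list begins "Cluster level covariates: IMD 2015, IDACI 2015, baseline rate of health service use endpoint" and goes on to cluster size, outpatient referral rate and Borough. The data structure in the same section then puts "Number of HSU events during baseline period, Length of baseline period (days), Baseline rate of HSU events" into each child's record. These three fields are given no role in the model.

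Section 11.9 treats the questionnaire outcomes differently. Its child-level list ends "Borough, and the baseline questionnaire outcome score", and its cluster-level list ends "and the mean baseline questionnaire outcome score". No reason is given for the difference.

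Three other sections bear on the point:
- Section 7.1 defines baseline service use as annual rates for financial years 2014/15 to 2016/17, with 2016/17 alone where a single year is enough.
- Section 8.1 makes the cohort open.
- Section 15 adds interactions between arm and measures of disadvantage to the outcome models, with service-use rates among the outcomes.

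The SAP does not say which children supply the cluster baseline rate when the analysis is restricted to a tracer or single-condition population.

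**The concern.** Repeat service use tends to concentrate in the same children, so a child's own past use is likely to be among the strongest predictors of later use. A predictor that is already in the file but outside the model may leave estimates less precise than the data allow. Precision, not bias, is at stake.

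Where it could matter depends on the source of the variance. In the full population, clusters are large and differences between clusters dominate. In the smaller tracer and single-condition populations, variation between children carries more weight. In the equity interactions the comparison is mostly between children of the same cluster, where a cluster-level baseline rate explains nothing.

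**Working it through.** **1. The plan's own figure.** Section 5.1 claims over 87% power for a 20% reduction in non-elective admissions, with 11 clusters per arm, 3,800 children per cluster and a coefficient of variation k = 0.142. The admission rate is not printed, so the figure cannot be strictly reproduced; it can be tested for consistency. The Hayes-Bennett formula for rates, at two-sided 5% (assumed), is

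c = 1 + (z_α/2 + z_β)² [(λ0+λ1)/y + k²(λ0²+λ1²)] / (λ0−λ1)².

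With one year of follow-up, 87-88% power needs λ0 of about 0.053-0.062 per child-year. At 0.053, λ1 = 0.0424:
- Poisson term: 0.0954/3800 = 0.0000251
- between-cluster term: 0.020164 × 0.004607 = 0.0000929
- (λ0−λ1)² = 0.0001124
- z_α/2 + z_β = √(10 × 0.0001124/0.0001180) = 3.086, so power = Φ(3.086 − 1.96) = 87.0%

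The stated figure is plausible. The between-cluster term is 0.0000929/0.0001180 = 79% of the variance, and child-level covariates act mainly on the remainder.

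**2. Full population, arm effect.** Take Var(log rate ratio) = (2/11)[k² + 1/(nλt) + V(1−R)/n]. V is the variance of a gamma frailty between children, and R = s·Vλb/(1+Vλb) is the share explained by own baseline, with s the share of children who have a baseline and b its length in years. Assumed: n = 3,800, λ = 0.07/year, t = 2.25 years, V = 3, b = 1 year, s = 0.6.
- R = 0.6 × 0.21/1.21 = 0.104
- without own baseline: 0.02016 + 0.00167 + 0.00079 = 0.02262
- with own baseline: 0.02254
- reduction in standard error: 1 − √(0.02254/0.02262) = 0.2%

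**3. Tracer-sized populations, arm effect.** This formula gives no credit to the cluster baseline rate already in the model, so simulation is needed. Assumed: 22 clusters, k = 0.142, correlation 0.7 between a cluster's baseline and trial effects, 80% of children with a one-year baseline, 2.25 years of follow-up. A Poisson model with the cluster baseline rate was fitted with and without the child's own baseline. The table shows the standard deviation of the estimated log rate ratio.

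| n per cluster | rate/year | V | Cluster rate from same children | Cluster rate historical, all registered |
|---|---|---|---|---|
| 380 | 0.07 | 3 | 0.0824 → 0.0822 (0.1%) | 0.0826 → 0.0802 (2.9%) |
| 380 | 0.3 | 3 | 0.0621 → 0.0619 (0.3%) | 0.0642 → 0.0596 (7.1%) |
| 380 | 3 | 1 | 0.0475 → 0.0474 (0.2%) | 0.0512 → 0.0478 (6.7%) |
| 100 | 0.07 | 3 | 0.1448 → 0.1448 (0.0%) | 0.1461 → 0.1423 (2.7%) |
| 100 | 0.07 | 8 | 0.1619 → 0.1624 (−0.3%) | 0.1764 → 0.1649 (6.5%) |

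In the first row, power for a 20% reduction under the historical reading moves from 77% to 79%; in the second, from 94% to 96%. Runs at n = 100 with higher rates did not finish. Further simulations agree: changes of −0.2% to −2% (slightly worse) with the same-children rate, and gains of about 4-6.5% with a historical rate.

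**4. Equity interactions.** For a within-cluster contrast, cluster size and k largely cancel, and the standard error scales with √(1/(λt) + V(1−R)). With λ = 0.10, t = 3.25, b = 3 and s = 0.65 (all assumed), 1/(λt) = 3.077:
- V = 2: R = 0.65 × 0.6/1.6 = 0.244; reduction 1 − √(4.589/5.077) = 4.9%
- V = 4: R = 0.65 × 1.2/2.2 = 0.355; reduction 1 − √(5.659/7.077) = 10.6%

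Simulation with a binary disadvantage measure, a three-year baseline, 3.25 years of follow-up, 65-80% of children with a baseline, and the cluster rate built from the same children gave these falls in the interaction's standard deviation:
- n = 400, 0.10/year, V = 2-4: 5.1-9.4%
- n = 150, 0.15/year, V = 2-4: 7.4-14.3%
- n = 400, 0.30/year, V = 3: 14.2%

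A separate simulation (V = 3, 70% with a baseline) gave about 7-12% under either reading of the cluster rate.

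The printed standard error need not shrink. In one setting an ordinary Poisson fit reported 0.075 for the interaction, with or without own baseline, while the true standard deviation fell from 0.110 to 0.100 (9%).

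**5. Children without a baseline.** With uniform ages (assumed), those born after 31 March 2017 make up 3.25/18.25 = 18% of children ever under 16 in a window to June 2020 (section 8.1), or 4.25/19.25 = 22% to June 2021 (section 7.1), before counting children who move in.

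**The case against.** The strongest reply is that arm is a cluster-level variable and the model already carries a cluster baseline rate of the endpoint. If that rate is aggregated from the same children, it holds the baseline information that bears on the arm contrast. The stored child-level fields may exist for exactly that aggregation. This stands: under that reading the arm effect gains nothing. It does not reach the equity interactions, because a cluster rate cannot separate children within a cluster.

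The comparison with section 11.9 is also imperfect. Consented participants are asked to complete a baseline questionnaire, whereas the service-use cohort is open and many children have no baseline time. That is a plausible reason for adjusting at cluster level only, though the SAP does not give it, and a category for missing baseline time deals with it.

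A reader might infer that the omission appreciably widens the interval for the arm effect. A variance formula that ignores the cluster baseline covariate can suggest this, running from under 1% to over 20% depending on inputs. The documents do not support that reading: section 10.9 includes the covariate, and the largest values need a high-rate endpoint and strong, persistent differences between children. Nor does anything in the SAP suggest that the estimate is biased or that the primary population analysis is materially weakened.

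**Conclusion.** The omission is in the text and the point holds as a modest matter of precision.
- **Full population, arm effect:** negligible.
- **Tracer and single-condition populations, arm effect:** about nil if the cluster rate comes from the same children; about 3-7% of the standard error if it is historical or whole-population. Section 7.1's annual 2014-17 rates and the open cohort make the second reading plausible; the SAP does not settle it.
- **Section 15 interactions for service use:** the estimate is roughly 5-14% more precise under either reading. The gain lies in its true variability and may not show as a narrower printed Poisson interval.

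The SAP gives no tracer population size, no endpoint rate and no measure of how far a child's use persists over time. All sizes therefore rest on assumed inputs: 100-400 children per cluster in the subsets, 0.07 to 3 events per year, frailty variance 1-8, and 65-80% of children with a baseline.

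**What to change.** In section 10.9, add the child's own baseline use of the endpoint to the individual-level covariates, at least for the tracer, single-condition and equity models. One form is 0, 1, or 2 or more events, plus a category for no baseline time. Keep the cluster baseline rate, and state for each population in section 8 which children and which years it covers. If the sponsor prefers cluster-level adjustment only, the SAP should say so, so that use of the stored child-level fields is not left to a later choice.

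The cost is a line or two of text, since the fields are already in the stated data structure. The downside is that newborns and children who join later contribute no baseline information, and the model gains two or three parameters.

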11. PARTICIPANT-REPORTED OUTCOME DEFINITIONS AND ANALYSIS METHODS

11.1 Tracer condition analysis – Primary child outcome – PedsQL

The Pediatric Quality of Life Inventory (PedsQL) is a brief measure of health-related quality of life in children and young people. This will be completed at baseline and each follow up. In all instances, the outcome for analysis will be parent-reported and child-related. However, where appropriate, child-reported outcomes will also be collected and reported.

Age versions: 0-12 months, 13-24 months, 2-4 years, 5-7 years, 8-12 years, 13-18 years

For 0-12 months and 13-24 months:

Subscales: Physical Functioning, Physical Symptoms, Emotional Functioning, Social Functioning, Cognitive Functioning

Summary scores: Physical health summary score (mean of physical functioning and physical symptoms), Psychosocial Health (mean of emotional, social, and cognitive scales), Total Score (mean of all scales)

For age 2+:

Subscales: Physical functioning, Emotional functioning, Social functioning, School functioning

Summary scores: Physical health summary score, Psychosocial Health (mean of emotional, social, and school scales), Total Score (mean of all scales)

Mismatch of questionnaire version and participant age: Treat as missing any questionnaires for ages 8+ completed by children age 0-4 at baseline.

Total score: Sum of items divided by the number of items answered for all scales.

- Items: There are 21-45 items in the PedsQL, depending on age of CYP; each item assigned value of 0, 25, 50, 75, 100.
- Missing data: use the mean value for items within the subscale. If more than 50% missing in a subscale, exclude the participant's data.

To combine data across ages:

- Check distribution of scores; transform if needed.
- Convert scores to z-scores (number of SDs above/below the trial mean).
- Analyse follow-up z-score, adjusted for baseline z-score for individuals.

Primary Outcome: Total Score at 6-month follow-up

Secondary outcomes from PedsQL: Physical Health score, Psychosocial Health score, same analysis method.

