11.8 A School & Work Absence questionnaire

- How many days of school has your child missed due to ill health or attending health-related appointments in the past three months?
 - Number of days
 - Other responses
 - My child is too young to attend school
 - My child is school age but does not attend school for health reasons
 - My child is school age but does not attend school for other reasons
 - I can't answer this question
- How many days of work have you missed in the past three months due to your child's illness or healthcare appointments?
 - Number of days
 - Other responses
 - I am not working because of my child's health needs
 - I am not working for other reasons
 - I can't answer this question

We will report the number of missing days, and also treat the outcome as binary (any absence or no absence). The binary outcomes will be analysed using logistic regression and with chi-squared tests.

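### The PedsQL missing-item rule has no exception for a School subscale that does not apply, so children who attend no school can drop out of the primary child outcome

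*SAP*

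**What the plan says.** Section 11.1 lists the scales for children aged 2 and over as "Subscales: Physical functioning, Emotional functioning, Social functioning, School functioning". The two versions for infants under 2 have no school scale: "Subscales: Physical Functioning, Physical Symptoms, Emotional Functioning, Social Functioning, Cognitive Functioning". For missing items, the subscale mean is substituted up to a limit, and beyond it: "If more than 50% missing in a subscale, exclude the participant's data". The trigger is one subscale, and what is lost is described as the participant's data, not that subscale's score.

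The same section defines the total as "Total score: Sum of items divided by the number of items answered for all scales", which can be computed without school items. A few lines earlier it describes the total as the mean of the scales. The primary child outcome is given as "Primary Outcome: Total Score at 6-month follow-up", and the model is specified as "Analyse follow-up z-score, adjusted for baseline z-score for individuals".

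Section 11.8, the absence questionnaire, offers the responses "My child is too young to attend school" and "My child is school age but does not attend school for health reasons", and a third for school-age children not attending for other reasons. Section 8.4 admits consented children from birth to under 16. Section 21 starts from complete cases under missing completely at random. It names multiple imputation as the preferred method above 5% missing, but says only that it may be conducted.

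**The concern.** A School subscale left blank because the child attends no school is 100% missing and passes the 50% limit automatically. The missing items then reflect the child's age or health, not a poorly completed form. A 3-year-old at home, or a 10-year-old too unwell for school, could have every Physical, Emotional and Social item answered and still have no Total Score.

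The baseline score is a covariate, so a blank School subscale at baseline or at follow-up takes the child out of the complete-case model. A child who is under 2 at baseline and has turned 2 by follow-up meets the School scale for the first time at the outcome visit and can be lost there. Missing completely at random cannot hold for exclusions driven by age and by absence through illness. At stake are the population to which the primary child result applies and, to a lesser degree, its precision.

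**Working it through.** **1. Reproducing the planned size.** Inputs from SAP section 5.1: difference 4.5 points, SD 16.5, power 90%, ICC 0.02, 11 clusters per arm, 30% loss to follow-up, 1006 recruits per arm. A two-sided 5% test is assumed, because section 5.1 does not state one.

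- Without clustering: n = 2 × (16.5 × (1.960 + 1.282) / 4.5)² = 282.5, rounded up to 283 per arm.
- Children per cluster: m = n(1 − ICC) / (k − n × ICC).
- With k = 11: m = 277.3 / 5.34 = 51.9. Then 51.9 × 11 / 0.7 ≈ 816 per arm, which does not match.
- With k = 10, one cluster fewer as a small-number correction: m = 277.3 / 4.34 = 63.9, rounded to 64. Then 64 × 11 = 704 analysable and 704 / 0.7 = 1005.7, so 1006. This reproduces the plan.

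Section 5.1 attributes the 30% to loss to follow-up. It names no separate allowance for exclusion by a scoring rule.

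**2. Children lost under the rule.** The SAP gives no shares. Assume that 10–20% of consented children are preschool, that 30–60% of those attend no school or nursery, and that their school items are blank. The share lost is 0.10 × 0.30 = 3% to 0.20 × 0.60 = 12%. School-age non-attenders would add to this.

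- 1006 × 0.70 = 704 analysable per arm.
- 704 × 0.97 = 683.
- 704 × 0.88 = 620.

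**3. Effect on power.** With m the analysable number per arm divided by 11 and k = 10 as above, the variance of the difference is 2 × 16.5² × (1 + (m − 1) × 0.02) / (10 × m), and power = Φ(4.5 / SE − 1.96).

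| Lost | Analysable per arm | m | SE | Power |
|---|---|---|---|---|
| 0% | 704 | 64.0 | 1.387 | 90.1% |
| 3% | 683 | 62.1 | 1.396 | 89.7% |
| 12% | 620 | 56.3 | 1.427 | 88.4% |
| 20% (stress case) | 563 | 51.2 | 1.460 | 86.9% |

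The number of clusters dominates the variance, so losing children within clusters costs little.

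**4. Effect on whom the result describes.** If non-attenders are a share q and their true effect differs from that of attenders by d, the effect among those analysed differs from the effect in all consented children by q × d. Taking d = 4.5 points in either direction as an illustration, the difference is 0.05 × 4.5 = 0.23 points at q = 5% and 0.10 × 4.5 = 0.45 points at q = 10%. Both q and d are assumptions. If the effect is the same in both groups, the difference is zero.

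**5. Can the exclusion differ by arm?** There are three cases under the complete-case model with a baseline covariate.

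- Out of school at baseline, whatever happens later: no baseline score, so excluded in both arms.
- Attending at both visits: included in both arms.
- Attending at baseline and out of school at follow-up: excluded through the follow-up score.

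For children using a version with a School scale at both visits, only the third case can respond to the intervention.

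**6. Comparison within the SAP.** Section 11.4 handles the same problem for the SDQ more narrowly. Too many missing items in a subscale means that the total difficulties score is not calculated, and nothing is said about discarding the participant's other data.

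**The case against.** The SAP does not say how parents of non-attending children answer the school items, or whether the items are shown to them. The absence question in section 11.8 is a separate instrument, and being too young for school does not rule out nursery. This stands: the loss is possible, not certain, and its share is unknown.

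A reader might infer that the rule biases the trial against CYPHP, because ill children who return to school under CYPHP would enter its mean while their EUC counterparts stay out. The planned model does not allow that route. A child with a blank School subscale at baseline has no baseline score and drops out in both arms, returned or not. Only children who stop attending between baseline and follow-up could produce a difference between arms, and the document gives nothing from which to size it.

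A reader might also take it as settled that the Physical Health score is lost. The missing-data bullet stands under the Total Score heading, and the statement that secondary scores follow the same method may refer only to the regression. Loss of Physical Health is the literal reading, not the only one.

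Multiple imputation is the stated preference above 5% missing, a level that the planned 30% loss alone would pass. It could bring excluded children back, but it is optional. It also assumes missing at random, which is doubtful when absence through illness is related to the outcome itself.

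Finally, section 5.1 notes that power is understated because 23 clusters were randomised, and the precision loss is small in any case. That is accepted.

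**Conclusion.** The point holds as a defect in the scoring rule. As written, one inapplicable subscale can remove a child from the primary child outcome, against the section's own definition of the total over answered items and with no exception for non-attenders whom the SAP expects. The consequence is mainly representativeness: preschool children and children out of school through illness would be under-represented, in an analysis whose starting assumption cannot hold for them. The precision cost is minor, from about 90.1% power to 89.7–88.4% for an assumed 3–12% lost.

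This rests on school items being left blank and on assumed shares. The document does not support a claim of bias between arms or a serious loss of power. The change is still worth making before analysis, because it concerns a primary outcome and costs little.

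**What to change.** In section 11.1:

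- State that more than 50% missing in a subscale withholds that subscale score only.
- Calculate Physical Health from its own items in all cases.
- When School functioning is blank because the child does not attend, calculate the Total and Psychosocial scores from the items answered in the remaining scales, by the same rule at baseline and follow-up.
- Use the section 11.8 response to help identify non-attendance, noting that a child too young for school may still attend nursery.
- Add a sensitivity analysis of the primary outcome using only Physical, Emotional and Social items for all children aged 2 and over.

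The cost is SAP wording and scoring code, with no new data. The drawback is that some Total Scores will rest on three subscales, and a child may move between three and four across visits, which makes scores less comparable. The sensitivity analysis addresses this by using the same three scales for every child aged 2 and over.
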